9.5 Handling of Missing and Incomplete Data

Missing or incomplete data will be reported as deviations from the protocol.

9.6 Safety Evaluation

All randomized patients who take at least one dose of study medication will be included in the safety analysis. The incidence of adverse events, drug-related adverse events and premature discontinuations will be summarized descriptively for each treatment group. The incidence of treatment emergent ECG-findings and of abnormally high and low laboratory values will be presented by treatment group. Descriptive statistics for changes from baseline in vital signs and laboratory values will be presented by treatment group.

9.7 Evaluation of Immune Response

Patients will be included in the evaluation of immune response as outlined in section 9.4.

If appropriate, the results may be stratified for age, status of autoimmune antibodies and C-peptide levels at the entry into the study.

9.8 Evaluation of Clinical Efficacy

Patients will be included in the evaluation of clinical efficacy as outlined in section 9.4. If appropriate, the results may be stratified for time from diagnosis to visit 1, gender, age, status of autoimmune antibodies and C-peptide levels at the entry into the study.

The concentration-time courses of basal C-peptide secretion will be summarized separated by treatment. Standard parameters of descriptive statistics will be calculated for each of the sampling points and for the area under the C-peptide concentration curves. Means at any time will only be calculated, if at least 2/3 of the individual data were measured and were above the limit of quantification (LOQ). For the calculation of the mean value a data point below LOQ will be substituted by half of this limit. Where values below LOQ are included in the calculation of mean values, these means will be marked in the relevant summary table.

C-peptide values will be compared for the two treatment groups using standard statistical tests that will be specified in a statistical plan that will be amended. Area under the C-peptide curve of the MMTT will be analyzed as mentioned above. Other efficacy parameters like C-peptide at different sampling times, maximum C-peptide concentration or incremental area under the C-peptide curve may be calculated where appropriate.

Statistical analyses of weight corrected Insulin-doses, HbA1c, Serum-lipids and Serum-CRP levels will be done accordingly.

9.9 Interim Analyses

Informal interim safety analyses will be performed at 6-monthly intervals during safety discussions between the Study Committee and the independent external Safety Review Board. Decisions will be made on the discretion of the investigators and the

Safety Review Board. Any changes to the study as a result of the data review will be made as amendments to the protocol.

In addition an interim analysis for clinical efficacy and immunology parameters will be performed after 40 percent of both treatment groups have completed Visit 4 (12 months of treatment). For this analysis the statistical methods described above will be applied.

At this interim analysis the determination of sample size may be adjusted based on the clinical efficacy data so far obtained. If a clinically relevant and statistically significant difference for the primary efficacy endpoint can be assessed at this interim analysis, the study can be prematurely stopped by the discretion of the Study Committee and the Safety Review Board.

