9 STATISTICAL EVALUATION

9.1 Determination of sample size

For the primary endpoint the calculation of sample size is based on data on levels and variation taken from a recent study at the German Diabetes Clinic. After 12 months of intense insulin treatment, stimulated C-peptide was 0.37 ± 0.053 nmol/l (mean \pm standard deviation) With a sample size of 80 patients per group a 20% difference in stimulated C-peptide would be significant with a p-value < 0.01.

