13.4 Premature Discontinuation of the Complete Study

The study will be discontinued prematurely in the following cases:

- If undesirable effects that occur are so serious that the benefit-risk ratio is not acceptable.
- If the number of drop-outs is so high that correct completion of the study cannot realistically be expected.
- If a clinically relevant and statistically significant difference for the primary efficacy endpoint can be assessed at the interim analysis, as described in section 9.9). If the trial is prematurely terminated or suspended, Profil will inform promptly the investigators/institutions, and the regulatory authority(ies) of the termination or suspension and the reason(s) for the termination or suspension. The Ethics

suspension and the reason(s) for the termination or suspension. The Ethics Committee will also be informed promptly and provided with the reason(s) for the termination or suspension, as specified by the applicable regulatory requirement(s).

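### Section 9.9 allows an efficacy stop and an efficacy-driven sample-size change at 40% of patients, but fixes no significance boundary or method to control the type I error

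*Protocol*

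**What the plan says.** Section 9.9 places an efficacy and immunology interim analysis at the point where 40% of both treatment groups have completed Visit 4. On method it says: "For this analysis the statistical methods described above will be applied". The methods it points back to, in section 9.8, compare C-peptide between groups "using standard statistical tests that will be specified in a statistical plan that will be amended".

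Two decisions hang on this look:

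- **Sample size.** "At this interim analysis the determination of sample size may be adjusted based on the clinical efficacy data so far obtained".
- **Early stop.** "If a clinically relevant and statistically significant difference for the primary efficacy endpoint can be assessed at this interim analysis, the study can" be ended early at the discretion of the Study Committee and the Safety Review Board.

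Section 13.4 lists the same efficacy criterion under the lead-in "The study will be discontinued prematurely in the following cases", with a reference back to 9.9.

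No overall alpha or sidedness is given as a design parameter. The only significance level is in section 9.1: "With a sample size of 80 patients per group a 20% difference in stimulated C-peptide" "would be significant with a p-value < 0.01".

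**The concern.** The protocol itself settles that there is a comparative efficacy look, when it happens, what criterion stops the trial, and that the observed effect may change the sample size. It does not say what level counts as significant at the interim, what level remains for the final test, or how the final test is protected after a size change driven by the effect.

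A reader who follows 9.9 literally would run the ordinary test at 40%, stop if it is significant, and otherwise run the ordinary test again at the end, perhaps with a different number of patients. That gives two chances to declare success at a level meant for one. At stake is the primary claim of beta-cell preservation: a false positive would be more likely than the nominal level says, and an effect estimate reported after an early stop could be too large.

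**Working it through.** **Inputs**

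- Interim timing: 40% of each group (9.9). With 80 per group (9.1) that is 32 per arm.
- Mean 0.37 and SD 0.053 nmol/l (9.1). A 20% difference is 0.2 × 0.37 = 0.074 nmol/l.
- Allocation 1:1 (5.1).
- Alpha: not stated. Two-sided 0.05 and 0.01 are taken as the range.
- One test on one endpoint at each look is assumed.

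**The plan's own figure.** At 80 per group an observed difference of 0.074 gives z = 0.074 / (0.053 × √(2/80)) = 8.83, far beyond p < 0.01. The sentence in 9.1 is therefore true as worded, but it does not yield a design alpha or a power, so it cannot serve as an interim boundary.

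**Two looks at the same level.** The interim and final statistics Z1 and Z2 have correlation √0.40 = 0.632 under the null. The overall error is P(|Z1| > c) + P(|Z1| ≤ c and |Z2| > c).

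- c = 1.960: 0.0500 + 0.0363 = 0.0863.
- c = 2.576: 0.0100 + 0.0083 = 0.0183.

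Simulation with 2 million draws gave the same values, 0.0863 and 0.0183.

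**Effect of the clinical-relevance condition.** Suppose it means an observed difference of at least 0.074. At 32 per arm, √(2/32) = 0.25, so the interim z needed is 0.074 / (0.25 × SD), or 1.96 if that is larger. The final test stays at 0.05.

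| SD (nmol/l) | z for a 20% difference | Overall error |
|---|---|---|
| 0.053 (9.1) | 5.58 | 5.0% |
| 0.10 (assumed) | 2.96 | 5.1% |
| 0.15 (assumed) | 1.97 | 8.5% |
| 0.20 (assumed) | 1.48, so 1.96 binds | 8.6% |

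The condition stops mattering once the SD exceeds 0.074 / (1.96 × 0.25) = 0.151.

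**Adding an effect-driven sample-size change.** Let the final size be k times the plan and keep the conventional final test. Given the interim z1, the chance of rejecting in the upper tail is 1 − Φ((1.96√k − √0.4·z1) / √(k − 0.4)), plus the mirror term for the lower tail. Taking the largest value over the permitted k for each z1 and averaging over z1 between −1.96 and 1.96, then adding the 5% spent at the interim, gives these worst cases:

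- k from 1 to 2 (80 to 160 per arm): 9.6%.
- k down to 33/80 and up to 2: 10.1%.
- k down to 33/80, capped at 1: 9.1%.

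For nominal 0.01 and k from 1 to 2, the worst case is about 2 × 0.0104 = 2.1%.

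**Overestimation after an early stop.** With true difference δ = 0.074, SE = 0.25 × SD and a stop at z > 1.96, the mean estimate among stopped trials is δ + SE·φ(a) / (1 − Φ(a)), where a = 1.96 − δ/SE.

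| SD (nmol/l) | Mean estimate | Excess over 0.074 |
|---|---|---|
| 0.053 (9.1) | 0.0740 | about 0% |
| 0.10 (assumed) | 0.081 | 10% |
| 0.15 (assumed) | 0.104 | 40% |
| 0.18 (assumed) | 0.119 | 61% |

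**Boundaries that hold the overall error at 40% information**

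- Overall 0.05, O'Brien-Fleming-type spending: interim p < 0.0008 (z 3.357), final p < 0.0497 (z 1.962).
- Overall 0.05, Haybittle-Peto: interim p < 0.001, final p < 0.0496.
- Overall 0.05, equal boundaries: p < 0.0283 at both looks.
- Overall 0.01, O'Brien-Fleming-type spending: interim p < 0.00002, final p < 0.00999.

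**The case against.** The strongest reply is that the protocol defers the tests to a statistical plan, and boundaries are often set there. It never says that the tests are unadjusted or that no alpha is reserved. A reader might infer both, but the text is silent, and a later plan could add an adjustment. This stands as a limit on the claim. It does not remove the point, because the stopping criterion and the effect-driven size change are fixed in 9.9 itself, where the only guidance is that the same methods apply.

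A second reply is that significance alone does not stop the trial: the difference must also be clinically relevant and two bodies must agree. With the 20% difference and the SD of 9.1, the early look would add essentially nothing. This also stands, and it makes 8.6% an upper case. But relevance is not defined, its protection vanishes at an SD of about 0.15, and it does nothing about the size change. Discretion lowers the number of stops without controlling the error.

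Three further inferences go beyond the documents:

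- That an early stop would overstate the effect by some 60%. This needs an SD of 0.18, which appears nowhere in the protocol; at the stated 0.053 there is practically no excess.
- That the result after an early stop would rest on 32 per arm and simply discard the 18-month half of the primary endpoint. Section 9.4 defines the early-stop efficacy population as all patients who completed 12 months, so it may be larger than the interim cohort. That section does judge an early stop on 12-month completers, but it labels the 12-month visit as Visit 5, whereas 5.2 makes it Visit 4.
- That 9.9 and 13.4 flatly contradict each other on stopping. One is permissive and the other mandatory in wording, but 13.4 refers back to 9.9. The wording needs reconciling; it has no bearing on the size of the type I error.

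**Conclusion.** The point holds in a bounded form. As written, section 9.9 permits a stop for efficacy and a size change based on efficacy without naming any control of the type I error.

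If the same level is applied at both looks, the error rises to at most 8.6% for nominal two-sided 0.05, or 1.8% for 0.01, roughly 1.7- to 1.8-fold. Depending on what clinically relevant means and on the true SD, the early look alone could leave the error anywhere from about 5.0% to 8.6% at nominal 0.05. An effect-driven change up to twice the planned size, with a conventional final test, takes the worst case to about 9.6%, or about 10% if the size may also be cut.

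These figures assume a single endpoint test per look, an information fraction of 0.40, and an alpha that the protocol does not state. The overestimation is worth reporting only as a range, from about 0% at SD 0.053 to 61% at SD 0.18.

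**What to change.** 1. State the overall two-sided alpha in the protocol.
2. In 9.9, replace the unquantified reference to statistical significance with a fixed group-sequential boundary and the matching final level, and have 13.4 refer to it. For an overall 0.05, O'Brien-Fleming-type spending (0.0008 at 40%, 0.0497 at the end) or Haybittle-Peto (0.001 and 0.0496) would do; equal boundaries are also valid but take more from the final test. If the intended alpha is 0.01, the boundaries must be recomputed.
3. Define clinically relevant numerically if it is to remain part of the criterion.
4. Limit the sample-size change to a blinded re-estimate of the pooled SD. If effect-based changes are to be kept, prespecify the rule and a combination or conditional-error test. The boundaries in item 2 cover only the early look.
5. Reconcile the permissive wording of 9.9 with the mandatory wording of 13.4.

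The change is one of wording. With either of the first two boundaries the final level stays at 0.0496 to 0.0497 rather than 0.05, so almost no power is lost at the end. The real cost is that an early stop for efficacy becomes less likely.

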2.2 Administrative Structure

Principal Investigator: [name]. [name]

German Diabetes Clinic D-40225 Düsseldorf

Study Committee: [name]. [name]

[name]. [name]

[name]. [name]

German Diabetes Clinic D-40225 Düsseldorf

Coordinating Center Profil Institute for Metabolic Research GmbH

D-41460 Neuss

Safety Review Board: two independent outside expert and a representative of

Profil GmbH. All members of the Safety Review Board will be physicians who will otherwise not be involved in the conduction of the study. The members of the Safety Review Board will be appointed prior to study initiation.

This study is supported by an academic grant from Pfizer GmbH, D-76032 Karlsruhe

The German Diabetes Clinic will participate with approximately 25 to 35 patients.

Profil GmbH will serve as a coordinating center and will be responsible for

- study monitoring
- participation in site selection
- training and supporting the investigators and site staff in all study related procedures
- supplying sites with study medication and study materials
- labeling, packaging, storage, shipping and disposal of study medication
- randomization procedures

- design, distribution, review and archiving of CRF-documents
- participation in the external Safety Review Board
- data management
- quality assurance
- implementation of a service as a "Central Telephone Call-Center" for the study sites
- · collection of adverse events
- 24-hour-hotline for reporting of severe adverse events.

The Safety Review Board will consist of three physicians (two outside experts and a Profil representative). Informal safety analysis will be performed 6-monthly or more frequently, if required. The Safety Review Board will take part in an interim analysis after 40 percent of all participants will have completed twelve months of treatment. Randomization code will only be broken to investigators, if necessary for reasons of safety. Decisions will be taken on the discretion of the Safety Review Board and the Study Committee .Decisions will be protocolled. Any changes to the protocol as a result of the data review will be made as amendments to the protocol.

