5 OVERALL STUDY DESIGN AND PROCEDURES

5.1 Study Design

This study will be conducted as a randomized, double-blind, placebo-controlled, outpatient, parallel group study in adult patients with recent onset type 1 diabetes. Patients will be randomly assigned to treatment with either atorvastatin or placebo in a one-to-one manner. The treatment phase will be 18 months for each patient. Patients who are withdrawn from the study during the first nine months of the treatment phase will be replaced. A maximum of 160 patients will complete all study procedures. The number of subjects included may be adjusted following an interim analysis as specified in section 9.9)

Starting dose will be 40 mg per day of atorvastatin or a matching number of placebo tablets. After a run-in period of 4 weeks the daily dose will be increased to 80 mg per day or matching placebo. In case of side effects (e.g. myalgia) the dose will be reduced to 40 mg per day by the discretion of the investigator.

Efficacy on beta-cell preservation will be assessed by means of two-hour mixed-meal tolerance tests at baseline and after 12 months and 18 months of treatment. Safety data and data on metabolic control will be obtained at baseline and after 3, 6, 12 and 18 months of treatment.

Patients should continue insulin treatment throughout the study. A tight glycemic control should be aimed (Target HbA1c ≤ 6.5 %) from Visit 2 on.

5.2 **Study Flow Chart**

Visit	Screening	Visit 1 *	Visit 2	Visit 3	Visit 4	Visit 5	Early Discontinuation
Time	-28 to -2 days	0	3 months (±2 weeks)	6 months (± 10 days)	12 months (± 2 weeks)	18 months (± 2 weeks)	
Informed consent	х						
Inclusion/Exclusion Criteria	х						
Randomization		X					
Demographic Data	х						
Medical History and concomitant Illnesses	х						
2 h MMTT		X			х	х	
12 lead ECG	х					х	х
Vital signs	х	X	х	x	x	х	х
Body height ¹ , weight and BMI		х	х	х	х	х	х
Physical examination	х					х	x
Adverse Events		х	х	X	х	х	х
Concomitant Medication	х	х	х	х	х	х	х
Documentation of Insulin dose	Х	Х	х	х	х	х	х
Drug accountability		X	х	x	x	х	x
Hematology	х	х	х	х	х	х	х
Clinical Chemistry ¹	х	х	х	х	х	х	х
Serum Lipids	х	х	х	х	х	х	х
Coagulation	Х						
Urinalysis	х						
Transcriptional studies		х	х				
Cytokines/chemokines		Х	х		х	х	
Beta cell autoantibodies	х			х	х	х	
HCG ²	х	Х	х	х	х	х	х
Plasma CRP		х	х		х	х	
HbA1c	х	х		х	х	х	х
Fasting C-peptide		X³			X ³	X³	

Visit 1 only ²only female patients ³ sampled during mixed meal tolerance test

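### The Study Committee, based at a recruiting clinic, shares the decision to stop for efficacy at the interim, and nothing limits it to a recommendation without by-arm results

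*Protocol*

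**What the plan says.** Protocol 9.9 schedules an interim analysis of efficacy and immunology that "will be performed after 40 percent of both treatment groups have completed Visit 4 (12 months of treatment"). Section 5.1 states: "The treatment phase will be 18 months for each patient". The interim therefore falls while patients are still on blinded treatment.

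Two decisions hang on it:

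- **Stopping.** The condition in 9.9 reads: "If a clinically relevant and statistically significant difference for the primary efficacy endpoint can be assessed at this interim analysis". What follows when it is met is left to two bodies acting together: "the study can be prematurely stopped by the discretion of the Study Committee and the Safety Review Board". Section 13.4 lists the same ground for ending the study and refers back to 9.9.
- **Sample size.** "At this interim analysis the determination of sample size may be adjusted based on the clinical efficacy data so far obtained". Section 9.9 names no decider here. Section 2.2 leaves decisions to the Safety Review Board and the Study Committee, and 13.1 allows no protocol change without the Study Committee's agreement.

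Section 2.2 lists the Study Committee and the Principal Investigator at the same institution and adds: "The German Diabetes Clinic will participate with approximately 25 to 35 patients". The signature page includes the Principal Investigator among the Committee's signatories.

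The one safeguard placed beside the interim is in 2.2: "Randomization code will only be broken to investigators, if necessary for reasons of safety". Section 7.4 gives the purpose of blinding as less bias in collecting data and evaluating endpoints.

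**The concern.** A body that uses its own discretion on a treatment difference has to know that difference. Here the body sits at a clinic that is still treating and following trial patients, and the protocol sets no barrier between the interim comparison and that clinic.

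Knowledge of the emerging effect could act in three ways.

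- **Secondary endpoints.** These are insulin requirement and HbA1c (Synopsis). Both depend on how intensively insulin is managed, and study dose may be reduced at the investigator's discretion (5.1, 7).
- **Who is analysed.** Efficacy is analysed only in patients who complete (9.4). Under 6.5 the Study Committee itself determines which protocol violations are significant enough to allow discontinuation.
- **Later amendments.** A change in sample size agreed by people who may know the interim effect is open to the charge that the result drove it.

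**Working it through.** The protocol gives no figure to reproduce on this point. The check has two parts: reading the sections together, and sizing the exposure.

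**Is the interim by arm?** Section 9.9 applies the statistical methods described earlier in the chapter. Section 9.8 describes them as C-peptide summarised by treatment and compared between the two groups, with insulin dose, HbA1c, lipids and CRP handled in the same way. The stopping criterion is a between-group difference. So the interim is by arm.

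**Who acts on it?** Sections 9.9 and 2.2 name the Study Committee and the Safety Review Board jointly. Section 13.1 gives the Committee a veto over any amendment. No section says that the Board alone reviews the comparison, or that the Committee receives only a recommendation.

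**Does the code-break sentence in 2.2 close the gap?** No. It governs release of the randomization code. A table of group means breaks no patient's code, so the sentence neither forbids nor permits showing such a table to the Committee.

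**Size of the exposure**

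Inputs: up to 160 patients (5.1, 6.2), 80 per group (9.1), interim at 40% (9.9), 25 to 35 patients at the Committee's clinic (2.2), 18 months of treatment (5.1).

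- Interim size: 0.40 × 80 = 32 per group, or 64 of 160.
- Not yet at 12 months, whole trial: 160 − 64 = 96, or 60%.
- Clinic's share of the trial: 25/160 = 15.6% to 35/160 = 21.9%.
- Clinic's patients without a 12-month result, if its accrual runs in proportion to the trial's (assumption): 0.60 × 25 = 15 to 0.60 × 35 = 21. As a share of the trial: 15/160 = 9.4% to 21/160 = 13.1%.
- Clinic's patients without an 18-month result: at least those same 15 to 21. A patient just at Visit 4 has 18 − 12 = 6 months of blinded treatment left, so the number rises towards all 25 to 35 if few have reached month 18.

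If the clinic recruits earlier than the other sites, its numbers fall; if later, they rise.

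**The case against.** The strongest reply is that the protocol never says who prepares or receives interim tables. Section 2.2 names only the Safety Review Board as taking part in the interim analysis, and the Committee appears only where decisions are mentioned. A committee can decide on a board's advice without seeing data, and such arrangements are often left to an analysis plan or charter. This stands in part: a reader might infer that by-arm results are handed to the Committee, and no text says so. But the decision right is fixed in the protocol itself. It is a discretion shared on equal terms, not an act on advice.

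Three other strong readings are tempting and are not supported.

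- **Contradiction with 2.2.** The limit on code breaks concerns the code, so group summaries do not strictly contradict it. It leaves a gap; it is not a conflicting rule.
- **Investigators seeing by-arm data every six months.** Section 9.9 does say "Decisions will be made on the discretion of the investigators and the" Safety Review Board. That sentence concerns informal safety reviews, which are not stated to be by arm, and 2.2 names the Board and the Study Committee instead. It may be loose wording for the Committee.
- **All outstanding outcomes collected with knowledge of the interim.** Applying the 60% to every site would require about 20 sites to be informed. Only the Committee's clinic is shown to be exposed.

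Real protections also exist. Individual allocation stays masked, investigators do not see lipid results from Visit 1 on (8.9), C-peptide is measured centrally (8.16), and the HbA1c goal is the same for all (5.1, 8.3). The protocol gives Committee members' institution, not their clinical duties, so it is not documented that each of them treats trial patients. These points reduce the risk to the primary endpoint. They do not keep the Committee blind to the group difference.

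**Conclusion.** The concern holds as a flaw in decision rights. The protocol makes a Committee based at a recruiting clinic, with the Principal Investigator as a member, joint decider on an efficacy difference during double-blind treatment. It also gives that Committee a veto over a sample-size change based on efficacy data. Nothing limits it to a recommendation, which undercuts the purpose of blinding stated in 7.4.

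The exposure is moderate. The clinic accounts for 16-22% of patients. Under proportional accrual, 15 to 21 of them (9-13% of 160) would have the 12-month assessment still to come at the interim, and more the 18-month one. The percentages take 160 as the total and would be slightly lower if more patients are enrolled as replacements. The Committee's influence on completer status through 6.5 is not confined to its own clinic, but the protocol gives nothing from which to size it.

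The conclusion rests on one inference: exercising this discretion on its own judgement requires the Committee to know the difference. This should be corrected before the interim, because knowledge once shared cannot be withdrawn.

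**What to change.** Amend 2.2, 9.9 and 13.4 together:

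- By-arm interim efficacy results are prepared by a person who is already unblinded or otherwise not involved in study conduct. Section 7.5 already provides for such a person at the coordinating center.
- Those results are seen only by members of the Safety Review Board.
- The Board gives the Study Committee a recommendation (continue, stop, or change the sample size) without the results. The Committee keeps its role under 13.1 but acts on that recommendation.
- The deciders for the 6-monthly safety reviews are reconciled: 9.9 names the investigators with the Board, and 2.2 names the Study Committee with the Board.

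The cost is protocol wording and a short charter for a Board that already exists; no new staff are needed. The drawback is that the Study Committee has to act on a recommendation without seeing the data. Re-estimating the sample size from the blinded pooled variance is an option that would remove by-arm data from that decision. It would change the method in 9.9, not just its wording, and the fix does not depend on it.
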